8.2.7.2. Work Productivity and Activity Impairment Questionnaire v2.0 in Chronic Hand Dermatitis

The Work Productivity and Activity Impairment Questionnaire is a patient-reported quantitative assessment of the amount of absenteeism, presentism, and daily activity impairment attributable to a specific health problem. The WPAI-ChHD is a 6-item questionnaire used to assess the impact of chronic hand dermatitis (ChHD, the same as CHE in this context) on job performance and productivity in the past 7 days (Reilly et al 2003).

8.3. Safety Assessments

Planned timepoints for all safety assessments are provided in the SoA (see Table 3).

See Section 6.5 for guidelines regarding the management of relevant laboratory or other safety assessment abnormalities.

8.3.1. Adverse Events

Adverse events will be monitored from the time the participant signs the ICF until at least 30 days after the last application of study drug. Adverse events for enrolled participants that begin or worsen after informed consent should be recorded on the Adverse Events Form in the eCRF regardless of the assumption of a causal relationship with the study drug. Conditions that were already present at the time of informed consent should be recorded on the Medical History Form in the eCRF. Adverse events (including laboratory abnormalities that constitute AEs) should be described using a diagnosis whenever possible rather than by individual underlying signs and symptoms.

Adverse events will be reported by the participant (or, when appropriate, by a caregiver, surrogate, or the participant's legally authorized representative). The investigator and any qualified designees are responsible for detecting, documenting, and recording events that meet the definition of an AE or SAE and remain responsible for following up on AEs that are serious, that are considered related to the study drug/procedures, or that caused the participant to discontinue the study drug. Care will be taken not to introduce bias when detecting AEs and/or SAEs. Open-ended and nonleading verbal questioning of the participant, such as "How are you feeling?", is the preferred method to inquire about AE occurrences. Adverse events may also be detected when they are volunteered by the participant during the screening process or between

visits or through physical examinations, laboratory tests, or other assessments. The definition, reporting, and recording requirements for AEs are described in Section 9.

All SAEs will be reported to the sponsor or designee immediately, without undue delay and no later than within 24 hours (see Section 9.4). The investigator will submit any updated SAE data to the sponsor or designee immediately, without undue delay and no later than within 24 hours of it being available.

After the initial AE/SAE report, the investigator is required to proactively follow each participant at subsequent visits/contacts. All AEs/SAEs will be followed until resolution, stabilization, the event is otherwise explained, or the participant is lost to follow-up (as defined in Section 7.3).

8.3.2. Physical Examinations

At the screening visit and the ET1 or ET2 visits, a comprehensive physical examination should be conducted. The comprehensive physical examination will include assessment(s) of the following organ or body systems: skin; head, eyes, ears, nose, and throat; thyroid; lungs; cardiovascular system; abdomen (liver, spleen); extremities; and lymph nodes; as well as a brief neurological examination. Fitzpatrick skin classification will be included as part of the physical examination at screening.

During the study, a targeted physical examination may be conducted by the investigator or medically qualified designee (per institutional policies and local standard of care) to assess AEs, symptoms/signs, laboratory abnormalities, or other findings. Findings from the targeted physical examination should be reported on the Adverse Events Form in the eCRF.

Height and body weight will be assessed at screening.

8.3.3. Vital Signs

Vital sign measurements (to be taken before blood collection for laboratory tests) include blood pressure, pulse, respiratory rate, and body temperature and will be taken at the timepoints indicated in the SoA (see Table 3). Blood pressure and pulse will be taken with the participant in the sitting position after 5 minutes of rest. Abnormal vital sign results identified after the first dose of study treatment, including those that worsen from baseline, considered clinically significant in the medical and scientific judgment of the investigator (ie, not related to progression of underlying disease) are to be reported as an AE.

8.3.4. Laboratory Assessments

See Table 8 for the list of clinical laboratory tests to be performed and Table 3 for the timing and frequency. A central laboratory will perform all clinical laboratory assessments for safety (eg, blood chemistries or hematology assessments) and will store the samples for PD analysis. Additional testing may be required by the sponsor based on emerging safety data. All Protocol-required laboratory assessments must be conducted in accordance with the Laboratory Manual and Table 3. Information regarding collection, processing, and shipping of samples for laboratory assessment is provided in the Laboratory Manual.

Clinically significant abnormal laboratory findings are those that are not associated with the underlying disease, unless judged by the investigator to be more severe than expected for the participant's condition. All laboratory tests with values considered clinically significantly

abnormal during participation in the study or within 30 days after the last application of the study drug should be repeated until the values return to normal or baseline or are no longer considered clinically significantly abnormal by the investigator or medical monitor.

It is not necessary to reassess chemistry or hematology at baseline (Day 1) if screening assessments were performed within 14 days of Day 1.

See Section 9.1 for information regarding laboratory abnormalities that should be recorded as an AE in the eCRF.

Table 8: Required Laboratory Analytes

Chemistry	Hematology	Serology	Pregnancy Testing
Albumin Alkaline phosphatase ALT AST Blood urea nitrogen or urea Creatinine Creatine kinase Glucose Total bilirubin Direct bilirubin (if total bilirubin is elevated above ULN)	Complete blood count, including: Hemoglobin Hematocrit Platelet count Red blood cell count Reticulocyte count White blood cell count Count Differential count (absolute and %), including: Basophils Eosinophils Lymphocytes Monocytes Neutrophils	HIV	Human chorionic gonadotropin (WOCBP only) FSH (women of nonchildbearing potential only)

Note: Additional tests may be required, as agreed by investigator and sponsor, based on emerging safety data or to rule out a diagnosis.

8.3.4.1. Pregnancy Testing

A serum pregnancy test will be required for all WOCBP during screening. Urine pregnancy tests will be performed locally, as outlined in the SoA (see Table 3), and as medically indicated (eg, in case of loss of menstrual cycle or when pregnancy is suspected).

If a urine pregnancy test is positive, the results must be confirmed with a serum pregnancy test. If the serum pregnancy test is negative after a urine test was positive, the investigator will assess the potential benefit/risk to the participant and determine whether it is in the participant's best interest to resume study drug and continue participation in the study.

[figure not shown]
If a pregnancy is confirmed by a serum pregnancy test, see Section 9.8 for reporting requirements.

8.3.4.2. Serology

HIV screening assessment will be performed at the screening visit to rule out HIV infection. Generally, serology tests should be performed early in the screening process due to the length of time needed to obtain the results. Additional tests may be performed if clinically indicated.

8.4. Pharmacokinetic Assessments

Pharmacokinetic parameters will not be evaluated in this study.

8.6. Unscheduled Visits

Unscheduled visits may occur at any time medically warranted. Any assessments performed at those visits should be recorded in the eCRF.

8.7. End of Treatment and Early Termination

A participant who completes the Week 16 visit will have reached the end of double-blind treatment (EOT1) with study drug. A participant who completes the Week 32 visit will have reached the end of open-label treatment (EOT2) with study drug.

If a decision is made that the participant will permanently discontinue study drug prior to the Week 32 visit, then the ET visit should be conducted. Assessments for the ET visit will be the same as those for Week 32. Early termination will be referred to as ET1 if it occurs before Week 16 or ET2 if it occurs after Week 16 and before Week 32. If the ET visit coincides with a regular study visit, then the ET evaluations will supersede those of that scheduled visit, and the data should be entered in the ET page in the eCRF. If this decision does not coincide with a regular visit, reasonable efforts should be made to have the participant return to the site to complete the ET procedures.

8.8. Follow-Up

The safety follow-up period is the interval between the Week 32 or ET visit and the scheduled follow-up visit, which should occur 30 days (+ 7 days' visit window) after the Week 32 or ET visit. All participants will have a safety follow-up visit 30 days (+ 7 days) following the end of treatment (Week 32/ET) to evaluate safety and disease control parameters. One exception to this would be for participants in the OLE period who have been in an observation/no treatment cycle with a total IGA-CHE score of 0 (clear) from Week 28 or earlier until Week 32; for such participants, the Week 32/ET visit will also count as the safety follow-up visit.

Adverse events and SAEs must be reported up until 1) 30 days after the last application of study drug or 2) until toxicities resolve, return to baseline, or are deemed irreversible, whichever is longer. Reasonable efforts should be made to have the participant return for the follow-up visit and report any AEs that may occur during this period.

9. ADVERSE EVENTS: DEFINITIONS AND PROCEDURES FOR RECORDING, EVALUATING, FOLLOW-UP, AND REPORTING

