	Days -28 to -1 Screening	Vehicle-Controlled Treatment						Open-Label Treatment		Safety Follow-Up	
		Day 1 Weeks						V	Veeks	Days	
Visit Day (Range)		Baseline	2a (± 3 d)	4 (± 3 d)	8 (± 3 d)	12a (± 3 d)	16 ^b /ET1 (± 3 d)	24a (± 3 d)	32/ET2° (± 3 d)	30 ^{a,d} (+ 7 d After Last Application)	Notes
Efficacy assessments (continued)					_					•
CHE-related Skin Pain NRS	X	Diary is	comple	ted each	evening f	from scre	ening throu	gh Week	32 or ET.		
DLQI		X	X	X	X	X	X	X	X		
PGIC			X	X	X	X	X	X	X	X	
QOLHEQ		X	X	X	X	X	X	X	X	X	
EQ-5D-5L		X	X	X	X	X	X	X	X		
WPAI-ChHD		X	X	X	X	X	X	X	X	X	
Laboratory assessmen	its										
Chemistry assessments	X	X*			X		X	X	X	X	*Not necessary if screening assessment performed within 14 days of Day 1.
Hematology assessments	X	X*			X		X	X	X	X	
FSH	X*										*Women of nonchildbearing potential only.
Serum pregnancy test	X										WOCBP will have a serum test at
Urine pregnancy test		X		X	X	X	X	X	X	X	screening and a urine test at other visits noted. A positive urine test must be confirmed by a serum test.
HIV serology	X										
PD and translational a	ssessments			•	•	•	•				
							_				

- ^a Visits at Weeks 2, 12, and 24 and safety follow-up can be performed virtually (through telemedicine if applicable) only due to COVID-19–related reasons. No efficacy assessments can be performed virtually (see Appendix B).
- b All Week 16 assessments must be completed before the participant can continue in the OLE. Study drug will not be applied in the clinic at Week 16 for participants not continuing into the OLE period.
- ^c Participants who withdraw early should complete the ET and the safety follow-up visits.
- d For participants in the OLE period who have been in an observation/no treatment cycle with a total IGA-CHE score of 0 (clear) from Week 28 or earlier until Week 32, the Week 32/ET visit will also count as the safety follow-up visit.

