6. STUDY TREATMENT

6.1. Study Treatment Administered

Ruxolitinib 1.5% cream or matching vehicle cream will be applied as a thin film BID, with applications at least 8 hours apart in the morning and in the evening at least 1 hour before bedtime.

On the first clinic visit day and subsequent in-house clinic visits, participants should not apply the study cream at home. The first application of the study cream on the day of the clinic visit will be done at the clinic.

At the baseline visit, an estimate of the %BSA to be treated (including hands and wrists [if applicable]) will be used by the IRT system to calculate the number of tubes of study cream to be dispensed. The participant will apply a thin film of study cream in front of site staff at the baseline/Day 1 visit by applying study cream until all the affected areas to be treated are covered. All areas identified at baseline should continue to be treated through the end of the DBVC period (Week 16) unless the participant meets criteria for stopping study cream. If there are new areas to be treated on the hands and wrists, including expansion of existing areas or development of new areas, after consultation with the investigator, study cream should be applied to these areas in addition to the areas treated at baseline, and the percentage of BSA to be treated will be recalculated and increased. This new estimate will be entered into the IRT system to calculate the number of tubes of study cream to be dispensed.

During the OLE period starting at the Week 16 visit, CHE lesions will be evaluated by the investigator to confirm whether the participant still requires continuation of therapy (IGA-CHE score ≥ 1) or can otherwise (re)enter the observation/no treatment cycle (IGA-CHE score = 0). At Week 16, the IRT system will dispense a prespecified number of tubes according to the assessment of total BSA affected.

Between OLE study visits, participants will self-evaluate recurrence of CHE (if applicable) and will treat all areas identified with active changes. If all signs and symptoms of CHE resolve between study visits, participants will stop treatment applications 3 days after they have disappeared. If this 3-day window is during a study visit and the IGA score for CHE (if applicable) is 0, as assessed by the investigator, treatment is to be stopped at the study visit.

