## 7.3. Analysis of the Primary Efficacy Parameters

## 7.3.1. Primary Efficacy Measures

## 7.3.1.1. Investigator's Global Assessment-Chronic Hand Eczema

The IGA-CHE is an overall eczema severity rating on a 0 to 4 scale that will be assessed during site visits. The grades for the IGA-CHE are shown in Table 3.

Table 3: Investigator's Global Assessment-Chronic Hand Eczema

Grade	Severity	Features	Intensity	
0	Clear	Erythema, scaling, hyperkeratosis/lichenification	Absent	
		Vesiculation, edema, fissures	Absent	
1	Almost	Erythema, scaling, hyperkeratosis/lichenification	At least 1 mild	
	clear	Vesiculation, edema, fissures	Absent	
2	Mild	Erythema, scaling, hyperkeratosis/lichenification	At least 1 mild	
		Vesiculation, edema, fissures	At least 1 mild	
3	Moderate	Erythema, scaling, hyperkeratosis/lichenification	At least 1 mild or moderate	
		Vesiculation, edema, fissures	At least 1 moderate	
4	Severe	Erythema, scaling, hyperkeratosis/lichenification	At least 1 moderate or severe	
		Vesiculation, edema, fissures	At least 1 severe	

Source: Adapted from Ruzicka et al 2008.

The IGA-CHE-TS is defined as an IGA-CHE score of 0 or 1 with  $\geq$  2 grade improvement from baseline.

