#### 9.2. Adverse Events

#### 9.2.1. Adverse Event Definitions

A TEAE is any AE either reported for the first time or worsening of a pre-existing event after first application of study drug and within 30 days of the last application of study drug. For participants who crossover treatments, the first application date is period-specific, and the end date is 30 days after the last application date in this period, or the first application date in the next period, whichever comes first. Analysis of AEs (as discussed below) will be limited to TEAEs, but data listings will include all AEs regardless of their timing in relation to study drug application.

Adverse events will be tabulated by MedDRA PT and SOC. Severity of AEs will be graded using the NCI CTCAE v5.0 (Grade 1 to 5). The CTCAE reporting guidelines and grading details are available on the Cancer Therapy Evaluation Program website.

The subset of AEs considered by the investigator to be related to study drug will be considered treatment-related AEs. If the investigator does not specify the relationship of the AE to study drug, the AE will be considered treatment-related. The incidence of AEs and treatment-related AEs will be tabulated. Serious AEs will also be tabulated.

Any missing onset date, causality, or severity must be queried for resolution. Unresolved missing causality and severity will be handled according to the following rules:

- An unresolved missing causality will be considered treatment-related.
- An unresolved missing severity will be identified as an unknown severity.

For purposes of analysis, all AEs will be considered TEAEs unless the AE can unequivocally be defined as not treatment-emergent.

Application site reactions are AEs that occur at the site of drug application. A summary of ASRs will be provided.

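### The follow-up waiver can put the last planned safety contact 2 days (at most 5) short of 30 days off drug; secondarily, the protocol dates the follow-up visit from two different points

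*Protocol*

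**What the plan says.** Section 8.8 of the protocol gives every participant a safety follow-up visit, with one exception: those in an open-label no-treatment cycle at IGA-CHE 0 "from Week 28 or earlier until Week 32; for such participants, the Week 32/ET visit will also count as the safety follow-up visit". Footnote d to the Schedule of Activities (Table 3) repeats the exception: "from Week 28 or earlier until Week 32, the Week 32/ET visit will also count as the safety follow-up visit".

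The safety clocks run from the last application:

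- Section 8.8, reporting: "Adverse events and SAEs must be reported up until 1) 30 days after the last application of study drug", or until toxicities resolve, if that is longer.
- Section 8.3.1, monitoring: "until at least 30 days after the last application of study drug".
- SAP Section 9.2.1, which counts an event as treatment-emergent if it falls "within 30 days of the last application of study drug".

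Clearance between open-label visits is judged by the participant. Section 6.1 states: "If all signs and symptoms of CHE resolve between study visits, participants will stop treatment applications 3 days after they have disappeared". The IGA-CHE itself is a site rating; SAP Section 7.3.1.1 states: "The IGA-CHE is an overall eczema severity rating on a 0 to 4 scale that will be assessed during site visits". After Week 16, Table 3 schedules open-label visits only at Weeks 24 and 32.

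The follow-up visit is dated in two ways. Section 8.8 counts 30 days (+7) from the Week 32 or early termination (ET) visit. The Table 3 column heading counts 30 days (+7) from the last application, and Section 4.2 also counts from the last application.

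**The concern.** The follow-up windows have a plus side and no minus side, so 30 days off drug acts as a minimum everywhere except in the waiver. There, four weeks has been treated as if it were 30 days. For a participant who stopped at about Week 28, no planned contact covers the last days of the period in which treatment-emergent events are counted.

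Section 9.4 adds to this. It releases investigators from actively seeking SAE information once the safety follow-up visit, or 30 days from the last dose, has passed. If Week 32 counts as the follow-up visit, a site could read that release as starting before day 30.

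The two anchors are a matter of consistency. Two sites that each follow the protocol could see similar participants at different times off drug.

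**Working it through.** **Inputs.** Week 28 and Week 32 (Section 8.8, footnote d); the ±3-day window on Week 32 and on Week 24 (Table 3); 30 days (Sections 8.3.1 and 8.8, SAP Section 9.2.1). Study days follow SAP Section 4.1.2, so nominal Week w is Day 7w + 1: Week 28 is Day 197 and Week 32 is Day 225.

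**The plan's own figure.** Thirty days is a requirement, not a calculated value. The stated participation of about 40 weeks does reproduce: 4 + 16 + 16 + 30/7 = 40.3 weeks.

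**Waiver.** Let L be the study day of the last application and v the deviation of the Week 32 visit from nominal (−3 to +3). Days off drug at that visit are d = 225 + v − L, and the shortfall is 30 − d where that is positive.

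| Last application | Week 32 visit | Days off drug | Shortfall |
|---|---|---|---|
| Day 197 (Week 28) | nominal | 28 | 2 (2/30 = 7%) |
| Day 197 | 3 days early | 25 | 5 (5/30 = 17%) |
| Day 197 | 2 days late | 30 | none |
| Day 196 | nominal | 29 | 1 |
| Day 195 | nominal | 30 | none |
| Day 192 | 3 days early | 30 | none |

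A shortfall therefore needs a last application on Days 196–197 with a nominal visit, or on Days 193–197 with a visit 3 days early.

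**Who can be in that band.** A cycle confirmed at the Week 24 visit gives (32 − 24) × 7 = 56 days, or 56 − 3 − 3 = 50 if Week 24 is 3 days late and Week 32 is 3 days early. Neither falls short. The gap arises only for a participant who cleared and stopped after Week 24, close to Week 28. No scheduled visit rates IGA-CHE then, so qualifying for the waiver rests on self-assessed clearance under Section 6.1 or on an extra visit under Section 8.6 ("Unscheduled visits may occur at any time medically warranted").

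**Anchors.** Let g be the days from last application to the Week 32/ET visit. In days off drug, Table 3 gives 30 to 37 and Section 8.8 gives g + 30 to g + 37. The windows share a day only if g + 30 ≤ 37, that is, g ≤ 7.

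- g = 8: Section 8.8 gives 38–45 days.
- g = 15 (an ET visit just past the 2-week adverse-event interruption limit in Section 6.5.2): 45–52 days.
- g = 27: 57–64 days.

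Both rules give at least 30 days off drug at every g. For a participant treating up to Week 32, g is close to 0 and the two rules nearly coincide.

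**The case against.** The strongest reply is that the 28-day case is close to empty. The waiver asks for an IGA-CHE of 0, which is a site rating, and the last scheduled open-label rating before Week 32 is at Week 24, where no gap exists. Read strictly, a participant who cleared between visits may not qualify at all. This limits the reach but does not remove the fault: the text names Week 28, where no visit is scheduled, and Section 6.1 lets a no-treatment spell start on the participant's own judgement. A site could reasonably apply the waiver.

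A second reply is that the general duties survive. Section 8.3.1 requires monitoring to at least 30 days and Section 8.8 requires reporting to at least 30 days. The Week 32 visit already includes adverse-event review, vital signs, chemistry, hematology and a physical examination. This stands. A reader might infer that events in the last days go unreported or fall outside the treatment-emergent count; the documents do not support that. What is missing is a planned contact at which to ask about those days, and the wording of Section 9.4 keeps the surviving duty from closing the gap fully.

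On the anchors, a reader might infer that the conflict loses safety follow-up, or that Table 3 sets a visit that cannot be held because its window closes before Week 32 once g exceeds 37. The first does not follow, since both rules reach 30 days. The second reads a column heading very literally. Long unwaived gaps at Week 32 should also be uncommon, because Section 6.1 has participants restart treatment at the first sign of recurrence.

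**Conclusion.** Minor, and wrong as written. The waiver allows a final planned contact at 28 nominal days off drug, against a 30-day requirement: 2 days short nominally, 1 if the last application was the day before Week 28, and 5 at most. This takes Week 28 as nominal Day 197 and assumes that a site accepts clearance between visits as meeting the IGA-CHE condition. The documents do not say how many participants would fall in the band; the dates suggest few.

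The anchor mismatch is secondary and one of consistency only. The primary and key secondary analyses end at Week 16 and are not touched by either part.

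**What to change.** **Waiver.** In Section 8.8 and footnote d, replace the Week 28 condition with two that can be checked on the day: the last application recorded in the eDiary is at least 30 days before the actual Week 32 visit, and IGA-CHE is 0 at that visit. Otherwise the follow-up visit is held.

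The eDiary already records applications, so this changes wording only. A participant at 28 or 29 nominal days keeps the waiver if Week 32 is booked 2 days or 1 day late, inside its window. If it is not, one extra visit is needed. Under Section 8.8's timing, with g from 25 to 29, that visit falls between 25 + 30 = 55 and 29 + 37 = 66 days off drug. A lighter alternative is to keep the Week 28 rule and add a recorded adverse-event contact 30 to 37 days after the last application. For a Week 28 stop that is Days 227–234, or 2 to 9 days after nominal Week 32. A remote contact would need its own provision, because Table 3 footnote a allows a virtual follow-up visit only for COVID-19 reasons.

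**Anchor.** Use one rule in Section 8.8, Section 4.2 and the Table 3 heading; changing Table 3 alone would leave Section 4.2 in conflict. One workable rule is 30 days (+7) after the Week 32/ET visit, or after the last application if no ET visit is held. It never opens before the Week 32/ET visit and always gives at least 30 days off drug. The cost is that time off drug at follow-up still varies with g, as Section 8.8 already implies.
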